8.13 Safety Analyses

All Safety Analyses will be performed separately for Parts 1 and 2 for the following:

- Single-Blind Placebo Run-in Period for the Treated Safety Set (Part 1)
- Lixivaptan Titration Period for the Treated Safety Set (Part 1) and Lixivaptan Retitration Period for the Long-term Safety Set (Part 2)
- The Double-blind, Randomized Treatment and Follow-up I Periods for the Randomized Safety Set (Part 1) and the Maintenance Treatment and Follow-up II Periods for the Long-term Safety Set (Part 2)

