7.1. Disposition of Participants and Withdrawals

Disposition of participants in Part 1 will include, but not limited to, the following:

- The number of participants who
 - o Screened
 - Failed screening
 - Reasons failed screening
 - Placebo Run-in/Placebo Run-in Safety Set
 - Not completed
 - Reasons not completed
 - o Lixivaptan Titration/Lixivaptan Titration Safety Set
 - Not completed
 - Reasons not completed
- The number and percentage (percentage is calculated based on all the randomized participants) of participants who
 - Randomized/ITT
 - Treated/mITT/Randomized Safety Set
 - Completers/PEAS
 - On-treatment completers

- Off-treatment completers
- At least one on-treatment eGFR assessment/SEAS
- Discontinued from study drug early and reasons
- Not completed in Part 1 and reasons
- In PPAS

Disposition of participants in Part 2 will include, but not limited to, the following:

- The number and percentage (percentage is calculated based on all the continuing participants in Part 2) of participants who
 - Continued in Part 2
 - Treated/P2SS
 - At least 1 off-treatment eGFR/P2EAS
 - Discontinued from study drug early and reasons
 - Not completed in Part 2 and reasons

Note that Lixivaptan Treated Safety Set for Parts 1 and 2 combined consists of the participants who are randomized and treated (Randomized Safety Set) in lixivaptan treatment group in Part 1 and the participants who are treated (P2SS) in Part 1/Part 2 - Placebo/Lixivaptan cohort in Part 2.

7.2. **Protocol Deviations**

Protocol deviations will be tracked, recorded, and reviewed prior to database lock, following the Protocol Deviation Guidance Plan for this study.

Protocol deviations will be classified as "Important" or "Not Important".

Important protocol deviations include:

- Enrollment of a participant that did not meet inclusion criteria of the study/Enrollment of a participant that met exclusion criteria of the study.
- Missed safety assessments during Screening that are required for the thorough vetting of study inclusion/exclusion criteria are considered important deviations. They will be documented through failure of the respective Inclusion or Exclusion Criterion.
- Informed Consent Form (ICF) not obtained, or obtained after initiation of respective study procedures, important deviation from GCP consenting procedure, such as wrong version used, missing signature(s) and/ or date(s), ICF signed prior to IRB/IEC approval, other important deviation from GCP consenting process

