7.4. Exposure and Compliance

Exposure and compliance will be presented for Randomized Safety Set during the Double-Blind, Randomized Treatment Period (Part 1) and P2SS during the Maintenance Treatment Period (Part 2).

The duration of exposure will be presented in days and calculated as the date of last dose in treatment period minus the date of first dose in treatment period, plus one. Duration of exposure

and total dose taken (mg) will be summarized using descriptive statistics by treatment group (treatment cohort in Part 2).

Compliance to study drug is calculated by dividing the total capsules taken by the total capsules the participants were scheduled to take during the treatment period:

Treatment Compliance (%) = $\frac{total Capsules Taken}{Total Capsules Scheduled} \ge 100$

Dosing compliance will be summarized using descriptive statistics by treatment group (treatment cohort in Part 2). The number and percentages of participants who are < 80% compliant and $\ge 80\%$ compliant overall in the study will be summarized.

8. Efficacy Analysis

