8.12. Additional Analyses (Part 2)

Additional exploratory analyses may be conducted to address any issues caused by potentially different treatment/exposure patterns between Part 1 and Part 2 for the participants in the P2EAS.

9. Safety and Tolerability Analysis

Safety will be evaluated from reported AEs, changes in clinical laboratory values, changes in

vital signs, and electrocardiogram (ECG results).

A Safety Analyses will be performed for the following:

- Single-Blind Placebo Run-in Period for the Placebo Run-in Safety Set (Part 1)
- Lixivaptan Titration Period for the Lixivaptan Treated Safety Set (Part 1)
- Double-blind, Randomized Treatment and Follow-up I Periods for the Randomized Safety Set (Part 1)
- Maintenance Treatment and Follow-up II Periods for the P2SS (Part 2)
- Double-blind, Randomized Treatment and Follow-up I Periods and Maintenance Treatment and Follow-up II Periods for the LTSS (Part 1 and Part 2 combined)

The tolerability will be summarized by:

- Incidence of participants with the maximum dose level taken by the final tolerated dose level determined for the double-blind treatment period during Lixivaptan Titration Period
- Count and percentage of participants up-titrated, down-titrated, remaining unchanged, or discontinued by the dose levels by visit (or time after titration initiation) during Lixivaptan Titration Period
- Count and percentage of participants by dose level by Visit (or time after randomization) during the double-blind treatment period in Part 1 by treatment group
- Count and percentage of participants by dose level by Visit (or time after initiation of maintenance period) during the maintenance period in Part 2 by treatment group

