9.6. Lixivaptan Treatment Safety Analysis

The lixivaptan treatment safety will summarize the following safety information occurred post the first dose of lixivaptan treatment after randomization during the study based on the LTSS by treatment cohort and overall:

- Incidence of special liver events (ALT > 3 x, AST > 3 x, ALT or AST > 3 x, and Total Bilirubin > 2 x ULN)
- Kaplan-Meier product-limit curve for special liver events
- Summaries of TEAEs (see Section 9.2)

- Overall summary of TEAEs
- o TEAEs by preferred term and causality
- TEAEs by preferred term and severity
- Treatment-related TEAEs by preferred term and severity

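### The list of safety periods in SAP Section 9 omits the Part 2 Re-titration Period, which conflicts with protocol 8.13 and SAP 9.6

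*SAP*

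**What the plan says.** SAP Section 9 opens with five pairings of a study period with an analysis set. For Part 2 alone the entry is "Maintenance Treatment and Follow-up II Periods for the P2SS (Part 2". The pooled entry joins the double-blind and first follow-up periods of Part 1 to "Maintenance Treatment and Follow-up II Periods for the LTSS (Part 1 and Part 2 combined". Neither mentions re-titration.

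Protocol 8.13 does mention it. Its Part 2 periods include "Lixivaptan Retitration Period for the Long-term Safety Set (Part 2", separately from maintenance. SAP Section 15, which is meant to record departures from the protocol, logs the redefined Part 2 analysis sets but not the removal of this period.

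Other parts of the SAP point the other way. Section 9.6 summarizes "safety information occurred post the first dose of lixivaptan treatment after randomization during the study based on the LTSS by treatment cohort and overall". Section 7.1 confirms that the LTSS includes "the participants who are treated (P2SS) in Part 1/Part 2 - Placebo/Lixivaptan cohort in Part 2". Section 4.2.1.2 defines the key Part 2 liver endpoint over lixivaptan exposure in Part 2, and Sections 9.1 to 9.3 speak of Part 2 without limiting it to maintenance. Section 7.4, however, summarizes Part 2 exposure and compliance for "P2SS during the Maintenance Treatment Period" only.

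**The concern.** Re-titration is the period in which every Part 2 participant restarts lixivaptan after the drug-free follow-up and is stepped up toward the Part 1 dose level. For the former placebo arm it is the first lixivaptan since randomization. For a drug whose key safety question is liver injury, this window should be placed without ambiguity.

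Section 9 is the only place in the SAP that sets out safety analysis periods as a list, so a programmer could reasonably treat it as governing the tables in 9.1 to 9.3. Membership of the P2SS needs only one Part 2 lixivaptan dose (SAP Section 5), and that dose is taken in re-titration. Under the listed period, a participant who stops in re-titration counts in the denominator while the event that stopped them is not counted. A second programmer, working from 4.2.1.2, 9.1 or 9.6, would count it. The two could report different Part 2 incidences of ALT above 3 x ULN.

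**Working it through.** **Inputs.** Randomized: 1350; projected to continue: 90% (protocol 8.1). Allocation: 2:1. Re-titration: 2 to 4 weeks; maintenance: 52 weeks; Follow-up Period II: 4 weeks (protocol Table 4).

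**The plan's own figures.** 1350 x 0.90 = 1215, as stated. Part 2 length: 2 + 52 + 4 = 58 weeks and 4 + 52 + 4 = 60 weeks, matching the synopsis.

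**Size of the unlisted window.**
- Weeks covered by the Section 9 Part 2 entry: 52 + 4 = 56 of 58 to 60.
- Share of Part 2 lixivaptan time: 2/(2 + 52) = 3.7%; 4/(4 + 52) = 7.1%.
- Person-weeks: 1215 x 2 = 2430; 1215 x 4 = 4860.
- Former placebo arm, assuming equal continuation in both arms: 1215/3 = 405 participants, so 810 to 1620 person-weeks.

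**Direction of the effect.** Let N be the P2SS size, b the number with an event in maintenance or Follow-up II, and a the number whose only event is in re-titration. Incidence over all of Part 2 is (a + b)/N; over the listed period it is b/N. The difference, a/N, cannot be negative, so the listed period can only lower the reported incidence or leave it unchanged. Each such participant is worth 1/1215 = 0.08 percentage points overall and 1/405 = 0.25 percentage points in the former placebo cohort. The documents give no value for a.

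**Which window each text implies.**

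| Text | Re-titration included? |
|---|---|
| Protocol 8.13 | Yes, named |
| SAP 9, P2SS line | No |
| SAP 9, LTSS line | No |
| SAP 9.6 (LTSS) | Yes, by its start point |
| SAP 4.2.1.2, 9.1, 9.2, 9.3 | Yes, as no limit is stated |
| SAP 7.4 (exposure) | No |

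The LTSS thus has two windows within one section. For the former placebo cohort, 9.6 opens at the Visit 25 dose (protocol 6.6), whereas the Section 9 line next resumes at maintenance.

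**Exposure.** Section 7.4 computes duration from the first to the last dose within the period. A P2SS member who stops in re-titration has neither date in maintenance, so their Part 2 exposure is undefined.

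**Liver data at stake.** Protocol Table 4 schedules liver chemistry at Visits 27 and 29. Participants who finish re-titration in 2 weeks skip Visit 27, so they have only Visit 29.

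**The case against.** The strongest reply is that the table specifications, not the opening list, decide what is produced. Section 9.6 plans ALT and AST above 3 x ULN, bilirubin above 2 x ULN, Kaplan-Meier curves and TEAE summaries from the first lixivaptan dose after randomization. Section 9.2.1 tabulates discontinuation events for Part 2 without a period limit, 9.3 covers each scheduled time point, 7.1 counts early discontinuations and their reasons among all who continue, and all AEs are listed. This stands. A reader might infer from the list that re-titration events fall outside every planned safety table, but the documents do not support that.

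It does not remove the conflict. Section 9.6 contradicts the LTSS line of its own section. For the lixivaptan/lixivaptan cohort (about 1215 - 405 = 810) its clock starts in Part 1, so it yields no Part 2 incidence. It also omits the higher ALT and AST multiples and the Hy's Law count of 9.3.1. Those depend on how the Part 2 window is read.

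On exposure, the objection is partly right. Protocol Section 8 prescribes no exposure analysis, so 7.4 breaks no protocol rule. The reason to change it is to match exposure to the event window. Re-titration tolerability counts are likewise not required by protocol 8.13.

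**Conclusion.** The inconsistency is real. The Section 9 list departs from protocol 8.13 without being logged, conflicts with 9.6, and if followed would understate Part 2 AE and ALT incidence or leave it unchanged. It leaves the window for the key Part 2 liver endpoint open to two readings. The grade is minor to moderate.

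Two further inferences should be resisted. A reader might put a number on the participants whose stopping event would be lost; the documents give no stopping rate for re-titration, and 9.2.1 and 7.1 would still record such cases. A reader might also say that re-titration holds all of the Part 2 dose escalation; protocol 3.1.2 and the footnote to protocol Table 2 provide for attempts to re-establish dose levels during maintenance.

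The sizes rest on the planned 1215 and on equal continuation in both arms. In the event, SAP Section 12 reports 5 participants randomized, all ending in Part 1, so there are no Part 2 data and no result changes. The defect is in the plan as written.

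**What to change.** - In SAP Section 9, add a Part 2 entry for the Re-titration Period in the P2SS, as protocol 8.13 has for its Part 2 safety set, and insert re-titration in the LTSS line so that it agrees with 9.6.
- State once that the Part 2 windows for 9.1 to 9.3, including the ALT above 3 x ULN incidence and any Part 2 Kaplan-Meier curve, start at the first Part 2 dose at Visit 25.
- In Section 7.4, start Part 2 exposure at that same dose.
- If leaving re-titration out was deliberate, record it with a reason in Section 15 and reconcile 9.6.
- Optionally, add re-titration counts to the Part 2 tolerability summaries.

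The cost is SAP wording and a few table columns. No new data are needed. Reported Part 2 incidences could be slightly higher than under the listed periods.

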9.1. Key Liver Safety Analysis

The incidence of participants who develop serum ALT levels >3 x ULN will be summarized by treatment group for Part 1 and by treatment cohort for Part 2. For Part 1, Fisher's exact test will be used to test if the incidence rate in the lixivaptan group is different from that in the placebo group.

In addition, an eDISH plot will be presented for Part 1.

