1.9 Benefit/Risk Assessment

Safety data gathered to date in participants with ADPKD are consistent with the robust safety experience from lixivaptan treatment in studies in earlier indications investigated for lixivaptan—congestive heart failure, liver cirrhosis with ascites, or syndrome of inappropriate antidiuretic hormone secretion. The most common ($\geq 2\%$) adverse effects of lixivaptan are related to the exaggerated pharmacology of blockade of the renal concentrating mechanism. This results in urinary dilution with the production of increased amounts and frequency of urine output and, secondarily, the stimulation of thirst. No adverse effects on other body systems have been noted. Lixivaptan as a vasopressin V2 receptor antagonist is in the same pharmacological class as tolvaptan. DILI has been observed during the use of tolvaptan for ADPKD and JINARC/Jynarque[®] (brand names for tolvaptan) have boxed warnings for DILI in their Summary of Product Characteristics/US Prescribing Information. Although there have been no reports of DILI related to lixivaptan to-date, the potential risk of DILI during lixivaptan treatment exists; this protocol has been designed to frequently monitor the participants for liver test abnormalities, has established an IDMC for safety oversight and has established an independent Hepatic Event Review Committee to monitor and review any participant's signs, symptoms, and/or laboratory tests that meet hepatic event criteria, and described procedures to prevent liver toxicity. One of the two primary objectives of this study is to determine the risk of DILI as a result of lixivaptan treatment for ADPKD.

Additionally, pharmacodynamic data generated for vasopressin V2 receptor antagonists that assess the mechanism of action, primarily through the development program for tolvaptan, have been confirmed in Phase 2 studies with lixivaptan and support continued development of lixivaptan for this indication. As there additionally remains a large unmet medical need to address chronic treatment in patients with ADPKD, particularly those who have experienced liver chemistry abnormalities leading to discontinuation of treatment with tolvaptan, continued investigation of this drug for ADPKD is warranted. Based on the totality of evidence generated to date on lixivaptan, the benefit/risk assessment of lixivaptan remains favorable.

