3.7. Sample Size

Part 1:

Based on the results of the REPRISE trial with tolvaptan (Torres et al, 2017), it is assumed that the standard deviation for the primary efficacy endpoint, change from baseline to post-treatment follow-up in mean eGFR, is 6.20 mL per minute per 1.73 m². Assuming a between-treatment group difference of -1.40 mL per minute per 1.73 m² and a randomization ratio of 2:1 for lixivaptan to placebo, a sample size estimate of 1314 participants (438 placebo-treated participants and 876 lixivaptan-treated participants) is required to achieve 90% power at a significance level of 0.01. This estimate has been adjusted up to 1350 participants (450 placebo participants and 900 lixivaptan participants). It is estimated that approximately 2250 participants will need to be screened in order to randomize 1350 participants.

Part 2:

This is a convenience sample based on the number of participants who elect to continue into Part 2. It is estimated that approximately 1350 participants will be randomized in Part 1. All participants except those who discontinue due to an adverse event or withdraw consent will continue into Part 2. Approximately 90% (1215) of Part 1 participants are anticipated to continue into Part 2.

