6.1.3. Multiple Comparisons

To control the family-wise type I error at the pre-specified level (≤ 0.01), the primary and secondary endpoints in Part 1 will be tested in hierarchical order:

- Treatment difference for the primary endpoint must be statistically significant (p-value ≤ 0.01)
- Treatment difference for annualized rate of change (slope) in on-treatment eGFRs is tested only if treatment difference for the primary endpoint is statistically significant (p-value ≤ 0.01)
- Treatment difference for annualized percent change from baseline in htTKV is tested only if treatment difference for annualized rate of change (slope) in on-treatment eGFRs is statistically significant (p-value ≤ 0.01)

Because the testing is sequential, the type I error rate of ≤ 0.01 is maintained. Failure at any stage in the sequence implies automatic failure at all subsequent stages. All p-values for each comparison without adjustments will be provided in the summary tables for informational purposes.

No adjustments will be made for multiple comparisons for other endpoints.

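### The only formal comparison for the key liver endpoint is a Fisher test of difference, with no effect estimate or confidence interval to show how large an excess risk Part 1 rules out

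*SAP*

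**What the plan says.** SAP 9.1 gives the incidence of ALT above 3 x ULN by treatment group, adds an eDISH plot, and for Part 1 states that Fisher's exact test "will be used to test if the incidence rate in the lixivaptan group is different from that in the placebo group". It gives no significance level, sidedness, margin, assumed rates, effect measure, interval or rule for reading the result. SAP 6.1.3 places everything outside the primary and secondary efficacy hierarchy under one sentence: "No adjustments will be made for multiple comparisons for other endpoints".

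Protocol 8.13.1.1 only summarizes the incidence by group and adds causality as judged by the hepatic events committee. SAP 9.3.1 adds higher ALT and AST multiples, Hy's Law cases and Kaplan-Meier time to first event by group. SAP 9.6 summarizes liver events in all randomized participants who received lixivaptan.

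On what the trial is meant to learn, Protocol 1.9 says: "One of the two primary objectives of this study is to determine the risk of DILI". Protocol Table 5 lists the clinical ALT rate on lixivaptan as not yet known and gives 4.4% for tolvaptan; the text of Protocol 1.4 gives 4.4-5.6%.

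**The concern.** The liver question is one of size: how often does lixivaptan raise ALT, and how much excess over placebo can be excluded? A p-value for a difference answers neither. If it is small, it does not say how large the excess is. If it is not, it does not say which excesses remain possible.

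The case for the drug in the protocol synopsis is that it may be safer for the liver than tolvaptan. An interval is what would let the trial support that, by excluding an excess of the size seen with tolvaptan, or show that it cannot. The efficacy analyses have this: the primary model code in SAP 8.2 requests confidence limits, and SAP 8.3.2 specifies a 99% interval for kidney volume. The key safety endpoint does not.

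**Working it through.** **The plan's own sample size.** It rests on eGFR alone (SAP 3.7): SD 6.20, difference 1.40, two-sided 0.01, 90% power, 2:1 allocation. Placebo n = (2.5758 + 1.2816)² × 6.20² × (1 + 1/2) / 1.40² = 14.88 × 38.44 × 1.5 / 1.96 = 437.7, so 438, and 3 × 438 = 1314. This matches the SAP and is then raised to 1350 (450 and 900). No liver rate enters it.

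**Inputs for the liver comparison.** From the documents: 450 placebo, 900 lixivaptan, a Fisher test of difference. Assumed, because the documents do not give them: placebo rate 1% (range 0.5-3%) and two-sided 0.05 (0.01, the efficacy level, also shown). All randomized participants are counted.

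**Power.** With X ~ Bin(450, p0) and Y ~ Bin(900, p1), power is the sum over all x, y of P(X = x) × P(Y = y) × 1[Fisher p(x, y) < alpha].

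| Lixivaptan rate, placebo 1% | Ratio | Power at 0.05 | Power at 0.01 |
|---|---|---|---|
| 2% | 2 | 23% | 7% |
| 2.5% | 2.5 | 43% | 20% |
| 3% | 3 | 64% | 38% |
| 4.4% | 4.4 | 96% | 85% |

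Power for a doubling at two-sided 0.05, by assumed placebo rate: 0.5%, 9%; 1%, 23%; 1.5%, 35%; 2%, 47%; 2.5%, 58%; 3%, 67%. Power against 4.4% on lixivaptan: 99.8% if placebo is 0.5%, 96% at 1%, 83% at 1.5%, 61% at 2%.

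**More participants are not the remedy.** For 80% power at 1% versus 2% (two-sided 0.05, 2:1), the pooled rate is (0.01 + 2 × 0.02)/3 = 0.01667. Placebo n = [1.96 × √(0.01639 × 1.5) + 0.8416 × √(0.0099 + 0.0098)]² / 0.01² = (0.3073 + 0.1181)² / 0.0001 = 1810, or 5430 in total.

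**What an interval would add.** Two illustrative outcomes, with Newcombe limits for the difference and score limits for the ratio:

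- 9/900 versus 4/450 (1.0% versus 0.9%): Fisher p = 1.0. Difference +0.1 points, 95% CI -1.3 to +1.2; ratio CI 0.37 to 3.43. Near-equal observed rates still leave a threefold rate possible.
- 18/900 versus 4/450 (2.0% versus 0.9%): Fisher p = 0.17. The Wilson limits are 1.269% to 3.139% and 0.346% to 2.263%. Lower limit: 1.111 - √[(2.000 - 1.269)² + (2.263 - 0.889)²] = 1.111 - 1.556 = -0.4 points. Upper limit: 1.111 + √[(3.139 - 2.000)² + (0.889 - 0.346)²] = 1.111 + 1.262 = +2.4 points. Ratio CI 0.80 to 6.32.

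If a tolvaptan-sized excess is taken as 4.4% minus the assumed 1%, or 3.4 points, both intervals exclude it. Neither excludes a doubling. The p-values 1.0 and 0.17 convey neither fact.

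**The case against.** The strongest reply is that the formal objective (Protocol 2.1.1, SAP 2.1.2) is only to compare incidences between the randomized groups. A two-group test with incidence by group does that. The documents pose no non-inferiority hypothesis, and the statement in Protocol 1.9 is benefit/risk background that does not match the formal list, where the liver objective is a key safety objective rather than a primary one. Liver injury itself is judged by blinded adjudication. With counts and denominators reported, any reader could compute an interval.

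Much of this stands. Fisher is the only formal test, not the only liver analysis, and the documents do not commit the sponsor to proving that the risk is low. What does not follow is that a test suffices. Comparing incidences calls for an estimated difference with its uncertainty, and none of the accompanying summaries is stated to give one. Leaving the interval to readers also leaves the main safety result unspecified in advance.

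The second illustrative outcome is open to the reply that it is already an observed 2.25-fold rate, so failing to exclude a doubling is unsurprising. That is fair; the near-equal outcome makes the same point without it.

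Two stronger readings are tempting. A reader might infer that the plan would treat non-significance as proof of liver safety; no passage says so and no decision rule is attached to the test. A reader might also infer that the test is weak against any doubling or larger effect. It is not: under the same assumptions power is 64% at threefold and 96% at 4.4%.

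**Conclusion.** The point holds as a gap in how the key liver result is specified. SAP 9.1 offers a test of difference and no between-group estimate or interval, so the result cannot say what excess has been ruled out. Assuming 1% on placebo and two-sided 0.05, power is 23% for a doubling and 43% for a 2.5-fold rate. The doubling figure depends heavily on the assumed placebo rate (9% to 67% over 0.5-3%) but stays below 80% throughout. A non-significant result would therefore be compatible with a doubling and could be misread.

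The practical consequence for this trial is limited. SAP section 12 records that it stopped with 5 participants randomized and that no statistical analyses will be done. The point matters for the plan as written and for any reuse of its text.

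**What to change.** In SAP 9.1, make the Part 1 risk difference in ALT above 3 x ULN, with a 95% Newcombe or Miettinen-Nurminen confidence interval, the main result. Keep the Fisher p-value as supporting, with its level and sidedness stated. Add one sentence saying that a non-significant difference is not a conclusion of liver safety. A ratio with a score interval is a useful companion because the rates are low.

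The cost is one table row and a sentence or two of text. It needs no new data, no more participants and no change to the efficacy hierarchy or its 0.01 level.

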8.13.1.2 Additional Liver Safety Analyses

The incidence of participants in Parts 1 and 2 who develop:

- >5 x-, 10 x-, and 20 x ULN elevations for ALT
- >3 x-, 5 x-, 10 x-, and 20 x ULN elevations for AST
- >3 x-, 5 x-, 10 x-, and 20 x ULN elevations for either ALT or AST
- Any elevation of bilirubin; elevated serum total bilirubin (TBL) to >2 x ULN
- Any elevation of alkaline phosphatase >1.5 x ULN
- Elevation of aminotransferase (>3 x ULN) accompanied by elevated bilirubin (>2 x ULN) and displayed as evaluation of Drug-Induced Serious Hepatotoxicity (eDISH) plots
- Elevation of aminotransferase in temporal association with nausea, vomiting, anorexia, abdominal pain, or fatigue
- Possible liver-related deaths and liver-related treatment discontinuations.

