- **Per-protocol Efficacy Analysis Set (PPAS):** The PPAS includes all participants in the PEAS who do not have any protocol deviations that are deemed to potentially impact efficacy.

Assignment of participants to populations will be confirmed at a blinded data review meeting to be held before the study database is locked for Part 1.

Part 2:

- **Part 2 Safety Set (P2SS):** The Part 2 Safety Set includes all participants who receive at least one dose of lixivaptan in Part 2.
- **Part 2 Efficacy Analysis Set (P2EAS):** The Part 2 Efficacy Analysis Set includes all participants in the Part 2 Safety Set who have at least one assessment of off-treatment eGFR in Part 2.

Parts 1 & 2 (Combined):

• Lixivaptan Treated Safety Set (LTSS): The Lixivaptan Treated Safety Set is defined as all participants who received at least one dose of lixivaptan treatment after randomization during the entire study. This analysis population will be used to summarize safety data during the study for all randomized, lixivaptan-treated participants.

6. General Issues for Statistical Analysis

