9.3.1. Special Liver Events

For Part 1 and 2, summarizes using incidence (rates) for participants with special liver events will be presented for all participants by treatment group (treatment cohort for Part 2) for the following:

- ALT > 5 x, 10 x, or 20 x ULN
- AST > 3 x, 5 x, 10 x, or 20 x ULN
- ALT or AST > 3 x, 5 x, 10 x, or 20 x ULN
- Total Bilirubin $> 2 \times ULN$
- Alkaline phosphatase >1.5 x ULN
- Hy's Law (ALT > 3 x ULN and Total Bilirubin > 2 x ULN)
- Elevation of aminotransferase in temporal association with nausea, vomiting, anorexia, abdominal pain, or fatigue
- Possible liver-related deaths and liver-related treatment discontinuations

A time to first event analysis will also be presented using Kaplan-Meier product-limit estimates by treatment group for ALT > 3 x, AST > 3 x, ALT or AST > 3 x, and Total Bilirubin > 2 x ULN.

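### The protocol plans eDISH liver plots for Parts 1 and 2; the SAP provides one for Part 1 only, narrows the combined criterion to ALT, and does not record either change

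*SAP*

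**What the plan says.** Protocol Section 8.13.1.2 opens its list of additional liver analyses with "The incidence of participants in Parts 1 and 2 who develop". One item on that list is "Elevation of aminotransferase (>3 x ULN) accompanied by elevated bilirubin (>2 x ULN) and displayed as evaluation of Drug-Induced Serious Hepatotoxicity (eDISH) plots". So the protocol's scope is both parts, its criterion is aminotransferase (not ALT specifically), and its display is the eDISH plot.

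The SAP deals with the same material in three places.

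- Section 9.1 summarises ALT above 3 x ULN for Part 1 by treatment group and for Part 2 by treatment cohort, then adds "In addition, an eDISH plot will be presented for Part 1". Part 2 is named for the incidence summary but not for the plot.
- Section 9.3.1 tabulates special liver events for each part. Its combined row is labelled Hy's Law and defined as "ALT > 3 x ULN and Total Bilirubin > 2 x ULN".
- Section 9.6 pools the two parts over the Lixivaptan Treated Safety Set, defined in SAP Section 5 as "all participants who received at least one dose of lixivaptan treatment after randomization during the entire study". Its liver item is "Incidence of special liver events (ALT > 3 x, AST > 3 x, ALT or AST > 3 x, and Total Bilirubin" above 2 x ULN. These are separate events, with no combined row and no plot.

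SAP Section 15 states that analyses deviating from the protocol are documented there. It lists neither the narrower eDISH scope nor the change from aminotransferase to ALT.

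**The concern.** Liver safety is the main reason for developing this drug as an alternative to tolvaptan, and Protocol Section 1.9 counts determining the DILI risk among the study's two primary objectives. An eDISH plot places each participant's peak aminotransferase against peak bilirubin. It therefore shows participants just short of either limit, which a threshold count cannot do.

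Under the SAP as written, that view exists for the first year only. It is absent for continuing participants' second year on drug and for placebo participants who start lixivaptan in Part 2. Two smaller gaps sit beside it. An AST-driven combined case would miss the combined row in either part. The pooled table gives each component separately, and separate counts cannot yield the number of participants meeting both.

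**Working it through.** **Inputs.** 1350 randomised 2:1, 900 to lixivaptan and 450 to placebo; about 90% (1215) continue into Part 2 (SAP Section 3.7). Double-blind and maintenance periods of 52 weeks each (Protocol Sections 6.4 and 6.7). Titration of 5 to 6 weeks and re-titration of 2 to 4 weeks (Protocol Sections 6.3 and 6.6). Dropout during Part 2 is not given, so it is assumed below.

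**The plan's own figure.** 0.90 × 1350 = 1215, as stated.

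**Person-time.** The Part 2 share is Part 2 lixivaptan weeks divided by Part 1 plus Part 2 lixivaptan weeks.

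- Full follow-up, post-randomisation only: Part 1 is 900 × 52 = 46,800; Part 2 is 1215 × 52 = 63,180. Share = 63,180 / 109,980 = 57.4%.
- Adding 6 weeks of titration for 1350 participants to Part 1 and 2 weeks of re-titration to Part 2: 46,800 + 8,100 = 54,900 against 1215 × 54 = 65,610. Share = 54.4%.
- Adding 5 weeks of titration and 4 weeks of re-titration: 46,800 + 6,750 = 53,550 against 1215 × 56 = 68,040. Share = 56.0%.
- Six weeks of titration, no re-titration, and an assumed 10% of Part 2 participants leaving halfway: 54,900 against 1215 × 0.95 × 52 = 60,021. Share = 52.2%.
- The same with an assumed 20% leaving halfway: 54,900 against 1215 × 0.90 × 52 = 56,862. Share = 50.9%.

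The titration variants treat pre-randomisation time as if it were on the Part 1 plot, which favours the SAP. If instead 10% of the lixivaptan arm leave Part 1 halfway and Part 2 is complete, the share rises: 1215 / (855 + 1215) = 58.7%.

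**Break-even.** Part 2 stops being the larger half when its mean exposure falls below 46,800 / 1215 = 38.5 weeks, or 54,900 / 1215 = 45.2 weeks with 6 weeks of titration counted in Part 1.

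**Head count.** Assuming 90% continuation in each arm, 0.90 × 450 = 405 placebo participants start lixivaptan in Part 2. The pooled set is 900 + 405 = 1305. Those 405 are 405 / 1305 = 31.0%; the other 900 (69.0%) appear on the Part 1 plot as lixivaptan-treated, for their Part 1 time.

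**Combined criterion.** A participant with AST above 3 x ULN, ALT at or below 3 x ULN and bilirubin above 2 x ULN meets the protocol's criterion. In SAP Section 9.3.1 that participant appears in the AST, ALT-or-AST and bilirubin rows, but not in the combined row.

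**The case against.** The strongest reply is that little information is lost. Section 9.3.1 counts combined ALT-plus-bilirubin cases in Part 2, with the two cohorts apart, so placebo crossovers and continuing participants can both be seen. ALT or AST above 3 x ULN or bilirubin above 2 x ULN is an adverse event of special interest in either part, reportable within 24 hours, and goes to blinded hepatic adjudication, whose results reach the IDMC and the safety report (Protocol Sections 7.3.7.1, 7.3.7.2 and 7.3.8.3). Individual laboratory listings are planned for both parts (SAP Section 9.3). All of this stands. A reader might infer that combined cases in Part 2 go unreported; the documents do not support that. What is missing is the planned graphical view and, in the combined row, AST-only cases.

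A second reply is that the protocol never asked for a pooled analysis. That is right: SAP Section 15 records the Section 9.6 summaries as an addition. Their lack of a combined row is not a departure from protocol, and adding one is an optional improvement. A pooled count is also nearly the sum of the by-part rows. It can differ only for someone meeting the criterion in both years, which the restrictions on resuming drug (Protocol Section 7.3.7.1) should make rare.

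Third, Protocol Section 8.14 lets the SAP modify the protocol's plans, so narrowing the display is allowed. The defect is that it was neither recorded nor justified. Finally, SAP Section 9.1 does not say that the plot is for Part 1 alone, and the figure shells are in a separate document. A Part 2 plot could be specified there, but the SAP text does not call for one.

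**Conclusion.** The point holds as an unrecorded difference between protocol and SAP on a key safety question. The eDISH display covers Part 1 where the protocol covers both parts, and the combined criterion uses ALT where the protocol says aminotransferase.

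The share of planned post-randomisation lixivaptan person-time off the plot is about 57% with full follow-up, and 51–56% in the variants with titration or assumed Part 2 dropout. That is a modest majority, and it rests on the 90% continuation figure and on dropout patterns the documents do not give. A reader might take it to mean that most lixivaptan participants are missing from the plot. By head count the reverse is true: about 31% never appear as lixivaptan-treated, assuming equal continuation in both arms.

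No efficacy inference is affected. SAP Section 12 states that the study ended with 5 participants randomised, all terminated in Part 1, and that no statistical analyses will be performed. The point therefore bears on the plan as written, not on any reported result.

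**What to change.** - **SAP Section 9.1:** add an eDISH plot for the Part 2 Safety Set by treatment cohort, as the protocol plans.
- **SAP Section 9.3.1:** define the combined row as ALT or AST above 3 x ULN with total bilirubin above 2 x ULN, to match the protocol.
- **SAP Section 9.6 (optional):** add the same combined row and an eDISH plot for the Lixivaptan Treated Safety Set.
- **If the narrower scope is intended:** record it in SAP Section 15 with a reason.

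The cost is one figure, or two with the pooled plot, one redefined row and one optional row. The liver chemistry is already scheduled in both parts, so no new collection is needed.
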